4.5.3. Subjects Lost to Follow-up Prior to Last Scheduled Visit

A minimum of 3 documented attempts must be made to contact any subject lost to follow-up at any time point prior to the last scheduled contact (office visit or telephone contact). At least 1 of these documented attempts must include a written communication sent to the subject's last known address via courier or mail (with an acknowledgment of receipt request) asking that they return to the site for final safety evaluations and return any unused investigational product. If contact is made but the subject refuses or is unable to return to the site for the final safety follow-up visit, it should be documented in the eCRF.

4.6. Subject Numbering

[figure not shown]
During the screening visit, each subject will be assigned a unique 6-digit subject number by the Interactive Web Response System (IWRS). The subject number will consist of a 3-digit clinical investigational site number assigned by the sponsor, followed by a 3-digit subject number (e.g., 001) assigned by the study staff. This subject number will also serve as the screening number. A separate randomization number will be assigned once the subject is randomized, but the randomization number will not be used to track the subject. The unique 6-digit subject number will serve as the subject ID and be used to track the subject throughout the study. Each subject number will correspond with a treatment (active or PBO) as determined by the randomization schedule.

The clinical site is responsible for maintaining a current log of subject number assignments and bottle numbers of the investigational product administered to each subject. The unique subject number is required to be entered on all clinical investigation documentation (eCRFs, labeling of clinical materials and samples containers, drug accountability logs, etc.).

5. EXCLUDED, PRIOR, AND CONCOMITANT MEDICATIONS

The study physician should assess all concomitant medications at every visit, and at the screening visit in particular to ensure that the subject is not taking excluded medications.

5.1. Prior Medications

5.2. Concomitant Medications

Concomitant medications refer to all treatment taken between the date of the first dose of investigational product and the date of the last dose of investigational product. Concomitant treatment information must be recorded on the appropriate eCRF page. Concomitant as needed (PRN) topical and intranasal steroids for dermatologic reactions and allergic rhinitis are allowed and do not warrant exclusion from study. If the subject is currently taking an excluded medication at the time of the screening visit, then the subject must undergo a washout period equivalent to 5 half-lives of the drug before they may enter the prospective 6-week baseline period.

Use of dietary supplements or herbal preparations are permitted if subject has been using them consistently for more than 6 months prior to screening and does not plan on changing the dose for the duration of the double-blind phase. Use of St. John's Wort is not permitted (See [Section 12.1](#)).

Concomitant medications may be reduced or discontinued at the discretion of the investigator if medically warranted.

5.2.1. Concomitant AED Medications

Subjects participating in the study can take between 0-4 AEDs in addition to the investigational medication. Vagus nerve stimulator, ketogenic diet, and modified Atkins diet do not count towards this limit but must be unchanged for 3 months prior to the screening visit.

Subjects with surgically implanted VNS will be allowed to enter the study provided that all of the following conditions are met:

- The VNS has been in place for ≥ 1 year prior to the screening visit.
- The settings must have remained constant for 3 months prior to the screening visit and remain constant throughout the double-blind phase.
- The battery is expected to last for the duration of the double-blind phase.

Concomitant AEDs or their dose must be stable for 1 month prior to the screening visit and should not be changed at any time prior to Visit 5 in the double-blind phase but may be adjusted

during the open-label phase of the study. Concomitant AEDs may be reduced or discontinued at the discretion of the investigator if medically warranted.

Felbamate: The use of felbamate is allowed provided that the subject has been maintained on a stable dose of felbamate for > 6 months, and has had stable liver function (AST/ALT) and hematology during the course of treatment, and is expected to remain constant throughout the double-blind phase.

5.3. Rescue Medications

The use of rescue medication is allowed. The type, dose, date, and frequency will be recorded.

5.4. Excluded Medications

Excluded medications include all steroid medications, other investigational products, as well as ketoconazole. Concurrent use of ACTH, prednisone or other glucocorticoid is not permitted, nor use of moderate or strong inducers or inhibitors of CYP3A4/5/7. A list of CYP3A4/5/7 inhibitors and inducers is included in [Section 12.1](#). Moderate or strong inducer or inhibitor anti-epileptic drugs will be allowed (e.g., carbamazepine, phenytoin, etc.) Concomitant PRN topical and intranasal steroids for dermatologic reactions and allergic rhinitis are allowed and do not warrant exclusion from the study.

Only Epidiolex (cannabidiol; GW Pharmaceuticals, may go by another name in countries outside the US) is allowed during the double-blind phase provided the subject has been on a stable dose for at least 1 month prior to screening and is expected to remain on a stable dose without a foreseeable change for the duration of the double-blind phase. Other products containing THC or CBD are excluded in the double-blind phase of the study but allowed in the open-label phase. Tetrahydrocannabinol or CBD should be washed out for at least 6 weeks. Subjects with a positive result on THC or CBD test (via urine or plasma drug screen) at the screening visit, and a positive result on THC or CBD test (via plasma) at the baseline visit will be excluded from the study.

6. INVESTIGATIONAL PRODUCT

6.1. Identity of Investigational Product

Drug name: GNX suspension

Vehicle: The suspension contains GNX (50 mg/mL), hydroxypropyl methylcellulose, polyvinyl alcohol, sodium lauryl sulfate, simethicone, methylparaben, propylparaben, sodium benzoate, citric acid, and sodium citrate at pH 3.8 to 4.2, and is sweetened with sucralose and flavored with artificial cherry.

Strength: 50 mg/mL suspension; 110 mL in 125 mL high-density polyethylene bottles

PBO suspension

Vehicle: The PBO suspension consists of titanium dioxide, microcrystalline cellulose, sodium lauryl sulfate, simethicone, methylparaben, propylparaben, sodium benzoate, citric acid, sodium citrate and is sweetened with sucralose and flavored with artificial cherry.

Both GNX and PBO will be packaged in high-density polyethylene (HDPE) bottles with a child resistant closure.

GNX will be supplied at a concentration of 50 mg/mL (GNX equivalent) in 125 mL bottles, containing 110 mL GNX. A PBO suspension, which is identical in taste and appearance, will be supplied at an equal volume.

6.1.1. Blinding the Treatment Assignment

The contents of each bottle will be blinded using labels with unique bottle numbers. Only the investigational product supplier and the sponsor's investigational product manager will be unblinded as to the bottle number and the contents of each bottle of investigational product.

6.2. Administration of Investigational Products

6.2.1. Interactive Response Technology for Investigational Product Management

For the double-blind phase and the titration period of the open-label phase and thereafter an IWRS will be utilized for the following investigational product tasks:

- Randomization
- Supply management
- Inventory management and supply ordering
- Expiration date tracking
- Emergency unblinding

6.2.2. Allocation of Subjects to Treatment

Subjects will be randomly assigned at a 1:1 ratio (GNX: PBO) based on a randomization schedule at Visit 2 (Week 0). Subjects will be stratified into 2 groups based on baseline seizure frequency. Only the investigational product supplier and the sponsor's investigational product manager will be unblinded as to the contents of each bottle of investigational product. Study staff as well as subject and caregiver will be blinded to treatment assignments.

An IWRS will centrally randomize subjects. The randomization schedule will be generated using a standard, validated method and maintained by the investigational product supplier and IWRS vendor. The investigator will be instructed by the IWRS, which numbered bottle to use to dose a subject. The investigator and research staff will be aware of the ascending dose design of the clinical investigation; however, the investigator, the research staff, and the subjects will be blinded with respect to who is receiving active drug versus PBO. The maximum PBO period is 17 weeks.

The contents of each bottle will be blinded using labels. The randomization schedule will match a subject number to a bottle number. Upon completion of baseline evaluations for each subject, the investigator or appropriate designee will log into the IWRS to receive a bottle number. Complete instructions for obtaining a bottle number will be provided to the clinical sites prior to initiating the study. The designated personnel at the clinical site will match the assigned bottle number with the correct bottle of investigational product and distribute the bottle to the investigator or designee.

6.2.3. Dosing

Ganaxolone will be prescribed in increments of 15 mg/kg/day up to 63 mg/kg/day (maximum 1800 mg/day) as an oral suspension. Subjects ≤ 28 kg will be dosed on an mg/kg basis.

For subjects weighing ≤ 28 kg

Subjects weighing 28 kg (61.6 lbs.) or less will be dosed according to the subject's weight in kilograms and use oral suspension (Table 4). All investigational product prescribed per day will be administered in 3 divided doses following a meal or snack.

Table 4: Oral Suspension (50 mg/ml) Dosing for Subjects Weighing ≤ 28 kg

Dose	Total mg/kg/day	Days
6 mg/kg TID	18	1-7
11 mg/kg TID	33	8-14
16 mg/kg TID	48	15-21
21 mg/kg TID	63	22-28

TID = three times daily

For subjects weighing > 28 kg

Subjects weighing greater than 28 kg (61.6 lbs.) will be dosed by mg/day using oral suspension (Table 5). Suspension dosing will be administered in 3 divided doses following a meal or snack.

Table 5: Oral Suspension (50 mg/ml) Dosing for Subjects Weighing > 28 kg

Dose	ml per Dose	Total mg/day	Days
150 mg TID	3	450	1-7
300 mg TID	6	900	8-14
450 mg TID	9	1350	15-21
600 mg TID	12	1800	22-28

TID = three times daily

The maximum allowable dose is 63 mg/kg/day or a maximum of 1800 mg a day. Any subject not tolerating the next dose step can be maintained at the lower dose step for additional days before advancing to next dose. If the next dose is still not tolerated, they can drop back to the next lower dose step. A minimum dose of 33 mg/kg/day and 900 mg/day is generally required during the double-blind phase unless a lower dose is agreed to with the Sponsor. Dose changes, including alternative dosing paradigm (e.g., lower dose during the daytime and higher dose in the evening), should be discussed with the sponsor medical monitor prior to making the change or within 48 hours of making the change. The higher dose in the evening is expected to be better tolerated due to the proximity to bedtime. However, tolerability management and the final decision to adjust drug dosages lies with Principal Investigator.

Investigational product may be stopped immediately and without down titration in the case of an emergency, although a down titration in the event of an early termination is recommended. Dose de-escalation will occur in decreasing increments of 15 mg/kg/day or 450 mg every 4 days over 2 weeks whenever feasible.

Open-Label

Following the completion of the 17-week, double-blind phase, subjects randomized to PBO will transition to GNX while subjects randomized to GNX will stay on 63 mg/kg/day suspension (maximum 1800 mg/day or Maximum Tolerated Dose [MTD]). Subjects will begin the 4-week blinded dose titration to 63 mg/kg/day or 1800 mg/day (or MTD) after completing Visit 5.

In order to maintain the blind of the double-blind phase, all subjects will be required to dose from 2 groups of bottles: Bottle Group A- maintenance and Bottle Group B- titration. In addition to the maintenance dose from Bottle Group A, subjects will be instructed to take a second dose from Bottle Group B. For subjects initially randomized to GNX, Bottle Group A will contain GNX while Bottle Group B will contain PBO. For subjects initially randomized to PBO, Bottle Group A will contain PBO while Bottle Group B will contain GNX.

Dosing from both Bottle Group A and Bottle Group B will begin at the end of Visit 5 (Week 17), the last visit in the double-blind phase, and continue until the end of the open-label 4-week titration period when subjects return to the site for evaluation (Visit 7, Week 21). Subjects will have an interim safety visit at Visit 6 (Week 19) 2 weeks after starting the open-label phase in which they will receive a new set of medication bottles (Table 6).

**Table 6: Transition from Double-blind to Open-label: Oral Suspension (50 mg/ml)
 Dosing for Subjects ≤ 28 kg**

Titration Day	Bottle Group A- Maintenance	Bottle Group B- Titration
	DB GNX: GNX bottle	DB GNX: Placebo bottle
	DB Placebo: Placebo bottle	DB Placebo: GNX bottle
	Bottle Group A Dose	Bottle Group B Dose
1-7	63 mg/kg/day (21 mg/kg TID)	18 mg/kg/day (6 mg/kg TID)
8-14	63 mg/kg/day (21 mg/kg TID)	33 mg/kg/day (11 mg/kg TID)
Visit 6, Week 19	Safety visit and new set of Group A and Group B bottles issued	
15-21	63 mg/kg/day (21 mg/kg TID)	48 mg/kg/day (16 mg/kg TID)
22-28	63 mg/kg/day (21 mg/kg TID)	63 mg/kg/day (21 mg/kg TID)
Visit 7, Week 21	One set of GNX bottles dispensed, return to dosing from 1 bottle at a time	
	63 mg/kg/day (21 mg/kg TID)	

DB = double-blind; GNX = ganaxolone; TID = three times daily.

An example of the transition from double-blind to open-label dosing is shown in Table 7 for a 20 kg subject who was initially randomized to GNX during the double-blind phase.

Table 7: Example of Double-blind to Open-label: DB GNX Subject Weighing 20 kg- Suspension Dosing (50 mg/ml)

Titration Day	Bottle Group A- Maintenance Treatment: GNX	Bottle Group B- Titration Treatment: Placebo
Days 1-7	63 mg/kg/day (21 mg/kg TID)	18 mg/kg/day (6 mg/kg TID)
Day 1 morning dose	21 mg/kg; 8.4ml	6 mg/kg; 2.4ml
Day 1 afternoon dose	21 mg/kg; 8.4ml	6 mg/kg; 2.4ml
Day 1 evening dose	21 mg/kg; 8.4ml	6 mg/kg; 2.4ml
Continue dosing from Group A and B as above until the end of Day 7		
Days 8-14	63 mg/kg/day (21 mg/kg TID)	33 mg/kg/day (11 mg/kg TID)
Day 8 morning dose	21 mg/kg; 8.4ml	11 mg/kg; 4.4ml
Day 8 afternoon dose	21 mg/kg; 8.4ml	11 mg/kg; 4.4ml
Day 8 evening dose	21 mg/kg; 8.4ml	11 mg/kg; 4.4ml
Continue dosing from Group A and B as above until Visit 6, Week 19		
Visit 6, Week 19	Safety visit and receive new bottles	
Days 15-21	63 mg/kg/day (21 mg/kg TID)	48 mg/kg/day (16 mg/kg TID)
Day 15 morning dose	21 mg/kg; 8.4ml	16 mg/kg; 6.4ml
Day 15 afternoon dose	21 mg/kg; 8.4ml	16 mg/kg; 6.4ml
Day 15 evening dose	21 mg/kg; 8.4ml	16 mg/kg; 6.4ml
Continue dosing from Group A and B as above until the end of Day 21		
Days 22-28	63 mg/kg/day (21 mg/kg TID)	63 mg/kg/day (21 mg/kg TID)
Day 15 morning dose	21 mg/kg; 8.4ml	21 mg/kg; 8.4ml
Day 15 afternoon dose	21 mg/kg; 8.4ml	21 mg/kg; 8.4ml
Day 15 evening dose	21 mg/kg; 8.4ml	21 mg/kg; 8.4ml
Continue dosing from Group A and B as above until Visit 7, Week 21		
Visit 7, Week 21	One set of GNX bottles dispensed, return to dosing from 1 bottle at a time	
Day 29	63 mg/kg/day (21 mg/kg TID)	
Day 29 morning dose	21 mg/kg; 8.4ml	
Day 29 afternoon dose	21 mg/kg; 8.4ml	
Day 29 evening dose	21 mg/kg; 8.4ml	

DB = double-blind; GNX = ganaxolone; TID = three times daily.

An example of the transition from double-blind to open-label dosing is shown in Table 8 for a 20 kg subject who was initially randomized to PBO during the double-blind phase.

Table 8: Example of Double-blind to Open-label: Placebo Subject Weighing 20 kg- Suspension Dosing (50 mg/ml)

Titration Day	Bottle Group A- Maintenance Treatment: Placebo	Bottle Group B- Titration Treatment: GNX
Days 1-7	63 mg/kg/day (21 mg/kg TID)	18 mg/kg/day (6 mg/kg TID)
Day 1 morning dose	21 mg/kg; 8.4ml	6 mg/kg; 2.4ml
Day 1 afternoon dose	21 mg/kg; 8.4ml	6 mg/kg; 2.4ml
Day 1 evening dose	21 mg/kg; 8.4ml	6 mg/kg; 2.4ml
Continue dosing from Group A and B as above until the end of Day 7		
Days 8-14	63 mg/kg/day (21 mg/kg TID)	33 mg/kg/day (11 mg/kg TID)
Day 8 morning dose	21 mg/kg; 8.4ml	11 mg/kg; 4.4ml
Day 8 afternoon dose	21 mg/kg; 8.4ml	11 mg/kg; 4.4ml
Day 8 evening dose	21 mg/kg; 8.4ml	11 mg/kg; 4.4ml
Continue dosing from Group A and B as above until Visit 6, Week 19		
Visit 6, Week 19	Safety visit and receive new bottles	
Days 15-21	63 mg/kg/day (21 mg/kg TID)	48 mg/kg/day (16 mg/kg TID)
Day 15 morning dose	21 mg/kg; 8.4ml	16 mg/kg; 6.4ml
Day 15 afternoon dose	21 mg/kg; 8.4ml	16 mg/kg; 6.4ml
Day 15 evening dose	21 mg/kg; 8.4ml	16 mg/kg; 6.4ml
Continue dosing from Group A and B as above until the end of Day 21		
Days 22-28	63 mg/kg/day (21 mg/kg TID)	63 mg/kg/day (21 mg/kg TID)
Day 15 morning dose	21 mg/kg; 8.4ml	21 mg/kg; 8.4ml
Day 15 afternoon dose	21 mg/kg; 8.4ml	21 mg/kg; 8.4ml
Day 15 evening dose	21 mg/kg; 8.4ml	21 mg/kg; 8.4ml
Continue dosing from Group A and B as above until Visit 7, Week 21		
Visit 7, Week 21	One set of GNX bottles dispensed, return to dosing from 1 bottle at a time	
Day 29	63 mg/kg/day (21 mg/kg TID)	
Day 29 morning dose	21 mg/kg; 8.4ml	
Day 29 afternoon dose	21 mg/kg; 8.4ml	
Day 29 evening dose	21 mg/kg; 8.4ml	

GNX = ganaxolone; TID = three times daily.

Subjects weighing > 28 kg and dosed using suspension will follow the dosing schedule in Table 9.

**Table 9: Transition from Double-blind to Open-label: Suspension (50 mg/ml)
 Dosing for Subjects > 28 kg**

Titration Day	Bottle Group A- Maintenance	Bottle Group B- Titration
	DB GNX: GNX bottle	DB GNX: Placebo bottle
	DB Placebo: Placebo bottle	DB Placebo: GNX bottle
	Bottle Group A Dose	Bottle Group B Dose
1-7	1800 mg/day; 12 ml per dose TID	450 mg/day; 3 ml per dose TID
8-14	1800 mg/day; 12 ml per dose TID	900 mg/day; 6 ml per dose TID
Visit 6, Week 19	Safety visit and new set of Group A and Group B bottles issued	
15-21	1800 mg/day; 12 ml per dose TID	1350 mg/day; 9 ml per dose TID
22-28	1800 mg/day; 12 ml per dose TID	1800 mg/day; 12 ml per dose TID
Visit 7, Week 21	One set of GNX bottles dispensed, return to dosing from 1 bottle at a time	
	1800 mg/day; 12 ml per dose TID	

DB = double-blind; GNX = ganaxolone; TID = three times daily.

An example of the transition from double-blind to open-label dosing is shown in Table 10 for a > 28 kg subject who was initially randomized to GNX during the double-blind phase using suspension.

Table 10: Example of Double-blind to Open-label: DB GNX Subject Weighing > 28 - Suspension Dosing (50 mg/ml)

Titration Day	Bottle Group A- Maintenance Treatment: GNX	Bottle Group B- Titration Treatment: Placebo
Days 1-7	1800 mg/day (600 mg TID)	450 mg/day (150 mg TID)
Day 1 morning dose	600 mg; 12ml	150 mg; 3ml
Day 1 afternoon dose	600 mg; 12ml	150 mg; 3ml
Day 1 evening dose	600 mg; 12ml	150 mg; 3ml
Continue dosing from Group A and B as above until the end of Day 7		
Days 8-14	1800 mg/day (600 mg TID)	900 mg/day (300 mg TID)
Day 8 morning dose	600 mg; 12ml	300 mg; 6ml
Day 8 afternoon dose	600 mg; 12ml	300 mg; 6ml
Day 8 evening dose	600 mg; 12ml	300 mg; 6ml
Continue dosing from Group A and B as above until Visit 6, Week 19		
Visit 6, Week 19	Safety visit and receive new bottles	
Days 15-21	1800 mg/day (600 mg TID)	1350 mg/day (450 mg TID)
Day 15 morning dose	600 mg; 12ml	450mg; 9ml
Day 15 afternoon dose	600 mg; 12ml	450mg; 9ml
Day 15 evening dose	600 mg; 12ml	450mg; 9ml
Continue dosing from Group A and B as above until the end of Day 21		
Days 22-28	1800 mg/day (600 mg TID)	1800 mg/day (600 mg TID)
Day 15 morning dose	600 mg; 12ml	600 mg; 12ml
Day 15 afternoon dose	600 mg; 12ml	600 mg; 12ml
Day 15 evening dose	600 mg; 12ml	600 mg; 12ml
Continue dosing from Group A and B as above until Visit 7, Week 21		
Visit 7, Week 21	One set of GNX bottles dispensed, return to dosing from 1 bottle at a time	
Day 29	1800 mg/day (600 mg TID)	
Day 29 morning dose	600 mg; 12ml	
Day 29 afternoon dose	600 mg; 12ml	
Day 29 evening dose	600 mg; 12ml	

DB = double-blind; GNX = ganaxolone; TID = three times daily.

An example of the transition from double-blind to open-label dosing is shown in Table 11 for a > 28 kg subject who was initially randomized to PBO during the double-blind phase using suspension.

Table 11: Example of Double-blind to Open-label: Placebo Subject Weighing > 28 kg- Suspension Dosing (50 mg/ml)

Titration Day	Bottle Group A- Maintenance Treatment: Placebo	Bottle Group B- Titration Treatment: GNX
Days 1-7	1800 mg/day (600 mg TID)	450 mg/day (150 mg TID)
Day 1 morning dose	600 mg; 12ml	150 mg; 3ml
Day 1 afternoon dose	600 mg; 12ml	150 mg; 3ml
Day 1 evening dose	600 mg; 12ml	150 mg; 3ml
Continue dosing from Group A and B as above until the end of Day 7		
Days 8-14	1800 mg/day (600 mg TID)	900 mg/day (300 mg TID)
Day 8 morning dose	600 mg; 12ml	300 mg; 6ml
Day 8 afternoon dose	600 mg; 12ml	300 mg; 6ml
Day 8 evening dose	600 mg; 12ml	300 mg; 6ml
Continue dosing from Group A and B as above until Visit 6, Week 19		
Visit 6, Week 19	Safety visit and receive new bottles	
Days 15-21	1800 mg/day (600 mg TID)	1350 mg/day (450 mg TID)
Day 15 morning dose	600 mg; 12ml	450mg; 9ml
Day 15 afternoon dose	600 mg; 12ml	450mg; 9ml
Day 15 evening dose	600 mg; 12ml	450mg; 9ml
Continue dosing from Group A and B as above until the end of Day 21		
Days 22-28	1800 mg/day (600 mg TID)	1800 mg/day (600 mg TID)
Day 15 morning dose	600 mg; 12ml	600 mg; 12ml
Day 15 afternoon dose	600 mg; 12ml	600 mg; 12ml
Day 15 evening dose	600 mg; 12ml	600 mg; 12ml
Continue dosing from Group A and B as above until Visit 7, Week 21		
Visit 7, Week 21	One set of GNX bottles dispensed, return to dosing from 1 bottle at a time	
Day 29	1800 mg/day (600 mg TID)	
Day 29 morning dose	600 mg; 12ml	
Day 29 afternoon dose	600 mg; 12ml	
Day 29 evening dose	600 mg; 12ml	

GNX = ganaxolone; TID = three times daily.

De-escalation Period

Any subject who completes the study or discontinues investigational product treatment should undergo a 2-week drug de-escalation (taper) period. The schedule will be dependent on the maintenance dose. Typically, doses will be reduced by 15 mg/kg/day or 450 mg/day every 3 days until the subject is completely off investigational product. Subjects should then return for a post-taper safety follow up visit.

Table 12: De-Escalation of Investigational Product

Formulation	Dose	Frequency
Suspension (weighing \leq 28 kg)	Reduce 15mg/kg/day	Every 3 days
Suspension (weighing $>$ 28 kg)	Reduce 450 mg/day	Every 3 days

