During the open-label phase, all subjects will be treated with GNX. Subjects will receive the same GNX dose given in the 17-week double-blind phase in the open-label phase of the study. However, to maintain the study blind, GNX subjects will enter into a 4-week false titration phase by increasing PBO doses in addition to maintaining GNX. Subjects who received PBO in the 17-week double-blind phase will enter a 4-week, GNX titration period in the open-label phase of the study.			
Reference Therapy, Dose and Mode of Administration: PBO is to be administered as an oral suspension with food during the 4-week, titration period of the double-blind phase of the study as follows:			

- PBO TID -Days 1-7
- PBO TID -Days 8-14
- PBO TID - Days 15-21
- PBO TID - Days 22-28

Placebo will only be used in the open-label phase of the study during the 4-week false titration phase for those subjects who were originally randomized to GNX in the 17-week double-blind phase.

Duration of treatment: Eligible subjects will collect 6 weeks of prospective baseline seizure data. Subjects will be randomized (1:1) to a 17-week double-blind treatment phase with GNX or PBO (4 weeks titration and 13 weeks dose maintenance), followed by a long-term open-label treatment phase with GNX. Following the completion of the 17-week double-blind phase, subjects randomized to PBO will transition to GNX (using false titration), while subjects randomized to GNX will stay on 63 mg/kg/day suspension (1800 mg/day maximum), or their Maximum Tolerated Dose (MTD). Subjects will begin the 4-week blinded dose titration to 63 mg/kg/day or 1800 mg/day (or MTD) after completing the final double-blind visit. It is estimated that the maximum duration of subject participation in the double-blind phase will be 23 weeks, including the 17-week double-blind treatment phase and 6-week prospective baseline period, and approximately an additional 3 years for the long-term open-label phase. The open-label phase will continue until the sponsor terminates the development of the investigational product in CDD or GNX has been approved and marketed in the subjects' respective country.

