3. STUDY DESIGN

3.1. Study Design and Flow Chart

This is a global, double-blind, randomized, PBO-controlled trial of adjunctive GNX treatment in children and young adults with CDD. The trial consists of a 6-week prospective baseline period to collect seizure data, followed by a 17-week double-blind treatment phase, which is then followed by a long-term open-label phase.

If available, a 2-month (8-week) daily historical seizure calendar will be reviewed at the screening visit to determine eligibility per inclusion/exclusion criteria. Acceptable historical seizure data must include seizure type, frequency, and denote seizure free days, with the historical seizure calendar starting at Week -14 (8-week historical + 6-week prospective = 14 weeks). Procedures specific to this protocol and not otherwise considered standard of care, will not be performed until written informed consent from the subject's parent or legally authorized representative (LAR) and/or subject assent has been appropriately obtained. In the event that parent/caregiver/LAR do not routinely maintain a daily seizure calendar per standard of care, written informed consent will be obtained from the parent/LAR and/or subject assent, and the subject will be asked to return to the clinic for the screening visit after they have maintained a 2-month (8-week) daily historical seizure calendar.

[figure not shown]
The double-blind phase includes 6 weeks prospective baseline, 4 weeks of titration followed by 13 weeks of dose maintenance. After meeting the eligibility criteria, approximately 100 children and young adults aged 2-21 years (inclusive) with CDD will be randomly assigned to receive GNX or PBO (1:1 ratio) for 17 weeks in addition to their standard anti-seizure treatment. Participants will be titrated to 63 mg/kg/day (max 1800 mg/day) over 4 weeks, and then maintained at that dose for another 13 weeks. Subjects who are not able to tolerate 63 mg/kg/day (or 1800 mg/day maximum) may be maintained on a lower dose after discussion with the sponsor. A minimum dose of 33 mg/kg/day or 900 mg/day is generally required during the double-blind phase unless a lower dose is agreed to with the Sponsor.

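### Tables 6 and 9 print only the full dose for the open-label transition, against the same-dose or MTD text for reduced-dose subjects, and no rule sets the Visit 7 dose when the two bottle-group volumes differ

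*Protocol*

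**What the plan says.** **Reduced doses are foreseen.** Protocol 3.1, like the Synopsis under Methodology, says that a subject who cannot tolerate the full dose "may be maintained on a lower dose after discussion with the sponsor". Protocol 6.2.3 gives a general double-blind minimum of 33 mg/kg/day and 900 mg/day, and lets the sponsor agree to less.

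**The open-label text follows the subject's own dose.** The Synopsis, under investigational product, dose and mode of administration, says: "Subjects will receive the same GNX dose given in the 17-week double-blind phase in the open-label phase of the study". Protocol 6.2.3 (Open-Label) has ganaxolone subjects stay on 63 mg/kg/day with the qualifier "maximum 1800 mg/day or Maximum Tolerated Dose [MTD", and attaches an MTD alternative to the blinded titration as well. The caregiver transition sheet in Appendix 3 says the Study Drug A dose does not change.

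**The titration target is not worded the same way everywhere.** The Synopsis (Methodology), Protocol 3.1 and SAP 1.3.1 have placebo subjects titrate up to 63 mg/kg/day, 1800 mg/day maximum, with no MTD alternative.

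**The schedules print one dose.** In Table 6 every Group A row reads "63 mg/kg/day (21 mg/kg TID", and the same dose stands under Visit 7, next to "One set of GNX bottles dispensed, return to dosing from 1 bottle at a time". In Table 9 every Group A row, and the Visit 7 dose, reads "1800 mg/day; 12 ml per dose TID". Neither table has a row or footnote for a lower dose. Table 9 is introduced as binding: "Subjects weighing > 28 kg and dosed using suspension will follow the dosing schedule in Table 9". Tables 7, 8, 10 and 11 are illustrations, for instance: "An example of the transition from double-blind to open-label dosing is shown in Table 7 for a 20 kg subject".

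**Bottles and blind.** For former ganaxolone subjects Group A is ganaxolone and Group B is placebo. For former placebo subjects it is the reverse. Protocol 6.1.1 and 6.2.2 list only the product supplier and the sponsor's product manager as knowing the bottle contents.

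**The concern.** A subject kept below full dose in the double-blind phase is one who was judged not to tolerate it. For that subject the schedule and the text give different Group A doses from the first transition day, and Table 9 is worded as something to be followed rather than as a default.

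The second problem comes four weeks later. Two bottle groups collapse into one at Visit 7. If the two volumes are not the same by then, continuing the current ganaxolone dose means knowing which group held ganaxolone. Staff at the site do not know this, and the documents name no step or role that supplies the answer.

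At stake are unintended dose changes, mostly in children, and open-label safety and efficacy summaries by former arm that may not reflect the dosing rule the text describes.

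**Working it through.** **1. Inputs.** Strength is 50 mg/mL (Protocol 6.1). The dose steps are 18, 33, 48 and 63 mg/kg/day (Table 4) and 450, 900, 1350 and 1800 mg/day (Table 5), each split over three daily doses. Group A and Visit 7 doses come from Tables 6 and 9.

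**2. Reproduce the printed volumes.** Volume per dose = mg/kg per dose × weight ÷ 50, or mg per dose ÷ 50.
- 20 kg at 21 mg/kg: 21 × 20 ÷ 50 = 8.4 mL (Tables 7 and 8 print 8.4).
- 15 kg at 21 mg/kg: 21 × 15 ÷ 50 = 6.3 mL (Appendix 3 prints 6.3).
- Above 28 kg: 600 ÷ 50 = 12 mL (Tables 5 and 9 print 12).

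The lower steps also match. The volumes are internally correct, so the problem is not arithmetic in the tables.

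**3. Schedule against text, former ganaxolone subject, transition Day 1.**

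| Double-blind dose | Dose under same-dose text | Dose in Table 6 or 9 | Difference | Ratio | Volume per dose |
|---|---|---|---|---|---|
| 33 mg/kg/day | 33 | 63 | +30 | 63/33 = 1.91 | 4.4 vs 8.4 mL (20 kg) |
| 48 mg/kg/day | 48 | 63 | +15 | 63/48 = 1.31 | 6.4 vs 8.4 mL (20 kg) |
| 63 mg/kg/day | 63 | 63 | 0 | 1.00 | 8.4 vs 8.4 mL (20 kg) |
| 900 mg/day | 900 | 1800 | +900 | 1800/900 = 2.00 | 6 vs 12 mL |
| 1350 mg/day | 1350 | 1800 | +450 | 1800/1350 = 1.33 | 9 vs 12 mL |

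The contradiction is confined to subjects below full dose. For them it is one or two of the plan's own dose steps, and more if the sponsor agreed to less than the general minimum.

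**4. Can the Group A and Group B volumes differ at the end of the transition?** Yes, on the documents' own wording. Group A can stay at a reduced dose (Synopsis, 6.2.3, Appendix 3) while Group B is taken up to 63 mg/kg/day (Synopsis Methodology, Protocol 3.1, SAP 1.3.1). If instead Group B stops at the same reduced dose, which the MTD wording in 6.2.3 permits, the volumes are equal.

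**5. What the single bottle then means.** Ganaxolone actually taken at the end of the transition is the Group A dose for a former ganaxolone subject and the Group B dose for a former placebo subject.
- A = B (33/33, 48/48 or 63/63): the ganaxolone dose is the same in either arm, and no unblinding is needed.
- A = 48, B = 63: it is 48 in one arm and 63 in the other.
- A = 33, B = 63: carrying A forward leaves a former ganaxolone subject unchanged and takes a former placebo subject from 63 to 33 (−30). Carrying B forward leaves the former placebo subject unchanged and takes the former ganaxolone subject from 33 to 63 (+30).

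The only Visit 7 dose printed is the full dose, which for a reduced-dose former ganaxolone subject is the step 3 contradiction again. The IWRS tasks listed in Protocol 6.2.1 do not include supplying a dose.

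**The case against.** The best reply is that these are incomplete tables, not rival orders. Tables 4 and 5 also print only the default schedule and leave dose reductions to the text. The MTD qualifier stands directly above Table 6. The investigator has the final say on dose, and the caregiver sheet says Study Drug A does not change. The site knows the subject's double-blind volume and can continue it without knowing what is in the bottle. On this reading a jump on Day 1 happens only if someone ignores several passages.

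Much of this stands, and it limits what can be claimed:
- A reader might infer that all six transition tables order full dose for everyone. Only Tables 6 and 9 are schedules; the other four are labelled examples.
- A reader might infer that a blinded site cannot resolve the conflict at all. For Group A it can. The blind matters only when the A and B volumes differ.
- A reader might infer that any single Visit 7 rule is wrong for one arm. That too is true only when the volumes differ.
- A reader might infer that an MTD found on placebo becomes the ganaxolone target. Protocol 6.2.3 does not say which MTD it means; it could be the dose tolerated during the open-label titration.

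What the reply does not remove is that Table 9 is worded as mandatory and has no exception, and that the investigator's authority does not supply the missing fact at Visit 7. SAP 1.2.5 remarks that the open-label phase is unblinded, but Protocol 3.1 has the IWRS keep the blind for the whole study, and 6.2.3 uses two bottle groups to protect it.

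**Conclusion.** The point holds in two parts. First, Tables 6 and 9 contradict the same-dose and MTD text for subjects below full dose: taken literally, a Day 1 change of 1.31 to 1.91 times at the 48 and 33 mg/kg/day steps, and 1.33 to 2.0 times at 1350 and 900 mg/day. Second, the plan has no carry-forward rule at Visit 7 when the bottle-group volumes differ. There is no gap for full-dose subjects, and no Visit 7 ambiguity when the volumes are equal.

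The number of subjects affected cannot be given, because the documents state no rate of reduced dosing. A count obtained by applying an assumed rate to all 100 subjects would also pool both arms, while the Day 1 jump reaches only former ganaxolone subjects.

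A reader might infer harm to the main result. There is none: under SAP 7.1 the double-blind seizure window ends the day before the first open-label dose. Former arms are not compared by a significance test in the open-label phase (SAP 7.2), and SAP 9 summarises the drug received. The effect is on open-label exposure, tolerability and safety, and on how those summaries are read. Because it concerns subjects already found not to tolerate full dose, and correcting it is a matter of documentation, it should be corrected. No view is given on which dose or rule is right.

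**What to change.** The sponsor should reconcile Tables 6 and 9, the example Tables 7, 8, 10 and 11, and the Appendix 3 transition form with the text in the Synopsis (Methodology; investigational product, dose and mode of administration; Duration of treatment), Protocol 3.1, Protocol 6.2.3 and SAP 1.3.1, for subjects who finish the double-blind phase below full dose. The reconciled text should say:

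- what applies to Group A, to Group B and at Visit 7 for these subjects;
- what the same ganaxolone dose and the MTD mean for former placebo subjects, and whether the MTD alternative applies to their titration;
- how the Visit 7 dose is determined when the Group A and Group B volumes differ.

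The mechanism for the last item must not reveal the double-blind assignment. An arm-dependent volume returned by the IWRS, for example, could let the site infer the arm from which of two different volumes comes back.

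The cost is a protocol amendment covering these tables and passages, a revised caregiver form, a matching SAP edit, and possibly an IWRS change, depending on the mechanism chosen. No extra visits or subjects are needed.
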